### 3.2 Rationale of study design

This study design is not randomized or double blind, but it has no bias since the patients themselves will be their own controls if they fulfill the enrollment criteria.

This study was designed since there is accumulating evidence that Th1 and Th17-type immunities play major roles in multiple sclerosis pathogenesis in the last decade. By contrast, Th2 and Treg cytokines appear to counterbalance the production of Th1 and Th17 cytokines and thus play an ameliorating role in the natural course of multiple sclerosis. Not surprisingly, many multiple sclerosis medications exert their beneficial effects through modulation of these cytokines. The effects of fingolimod on cytokine production are largely unknown. So this study was designed to see to evaluate the effects of fingolimod on cytokine production.

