## **9.5 Statistical model, hypothesis, and method of analysis**

There is no special hypothesis planned for this study.

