3 OBJECTIVES OF THE STUDY

3.1. PRIMARY OBJECTIVE

The primary objective of this study is to evaluate the differences between serum cytokine and chemokine levels of healthy controls and multiple sclerosis patients.

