5 ANALYZED POPULATIONS

The study will include only 80 relapsing remitting MS patients and 60 healthy controls without any known autoimmune disease. RRMS patients will be followed for 6 months.

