5.1. SAMPLE SIZE CALCULATION

Due to the lack of previous studies using all of the cytokines and chemokines and multitudinous analyses, it is difficult to estimate a precise sample size for our study. Despite this, our previous publications indicate that the basal IL-17 concentration is normally distributed with a mean of 32 pg/ml (\pm stdev of 15 pg/ml) in RRMS patients. If the true difference in the mean concentration of matched pairs is 7 pg/ml, we will need to study 50 pairs of subjects to be able to reject the null hypothesis with a power of 90%. The Type I error probability associated with this test of this null hypothesis is 0,05.

With assumption of drop out rate of 20% minimum 60 RRMS patients and 60 healthy control subjects should enroll to the study. Due to expected high rate of screen failure patients, we decided to screen 80 RRMS patients in order to reach 60 eligible RRMS subjects for the study.

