6.5 ASSESSMENT OF CYTOKINE AND CHEMOKINE LEVELS

6.5.1 ELISA

Subjects' **IL-4, IL-6, IL-8, IL-9, IL-10, IL-13, IL-17, IL-23, IFN- γ , TNF- α , VLA4, CCL2, CCL5, CXCR3 and CXCL13** values will be tabulated by calculating mean and standart error and compared as Control group vs. Visit 1 (MS patients), Visit 1 (MS patients) vs. Visit 2 (MS patients), Visit 1 (MS patients) vs. Visit 3 (MS patients) and Control group vs. Visit 3 (MS patients) by using appropriate statistical test. Mann Whitney U test with significance level of 0.05 was used for the independent variables since non-normal distributions had been observed. Wilcoxon test was used for the dependent variables with non-normal distributions. For the independent variables with normal distributions Independent Sample t test was used whereas Paired sample t test was used for the dependent variables with normal distributions.

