6.5.2 Flow Cytometry

Subjects' **IL-4, IL-6, IL-9, IL-10, IL-13, IL-17, IFN- γ and TNF- α** values will be tabulated by calculating mean and standart error and compared as Control group vs. Visit 1 (MS patients), Visit 1 (MS patients) vs. Visit 2 (MS patients), Visit 1 (MS patients) vs. Visit 3 (MS patients) and Control group vs. Visit 3 (MS patients) by using appropriate statistical test. Mann Whitney U test with significance level of 0.05 was used for the independent variables since non-normal distributions had been observed. Wilcoxon test was used for the dependent variables with non-normal distributions. For the independent variables with normal distributions Independent Sample t test was used whereas Paired sample t test was used for the dependent variables with normal distributions.

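### The serum comparison of controls with MS patients at Visit 1 is unadjusted for age and sex, and its stated power assumes matched pairs that the SAP neither defines nor analyses

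*SAP*

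**What the plan says.** The primary objective (SAP 3.1; Protocol 2.1) is to "evaluate the differences between serum cytokine and chemokine levels of healthy controls and multiple sclerosis patients". Protocol 1.2 describes the comparison with controls as one of basal levels, which is Control vs Visit 1.

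SAP 6.5.1 covers 15 serum analytes. For the comparisons between groups it states that "Mann Whitney U test with significance level of 0.05 was used for the independent variables since non-normal distributions had been observed", with an independent t test for normally distributed analytes. SAP 6.5.2 repeats this for flow cytometry: "For the independent variables with normal distributions Independent Sample t test was used". Neither section has a covariate, a stratum or a matched control-patient analysis.

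SAP 6.1 tabulates age and sex for both groups. Protocol 4.1 limits patients to 18-65 years and asks only that controls be over 18.

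Matching appears only in the sample-size text (SAP 5.1; Protocol 9.8): "If the true difference in the mean concentration of matched pairs is 7 pg/ml", 50 pairs give 90% power. The same text says "we decided to screen 80 RRMS patients in order to reach 60 eligible RRMS subjects for the study", whereas SAP 5 says "The study will include only 80 relapsing remitting MS patients and 60 healthy controls without any known autoimmune disease".

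Protocol 3.2 argues that the design is sound because "it has no bias since the patients themselves will be their own controls if they fulfill the enrollment criteria". Protocol 9.5 adds: "There is no special hypothesis planned for this study".

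**The concern.** A difference between controls and patients at Visit 1 will be read as a difference that goes with MS. If the groups also differ in age or sex, and an analyte depends on either, the planned tests cannot separate the two explanations, and a larger sample does not help. Confounding can create a difference or hide one.

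The own-control argument in Protocol 3.2 covers the visit-to-visit contrasts within patients, which this point leaves untouched. It does not cover controls against patients.

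The sample-size text raises a second question. If it describes control-patient pairs, the planned tests do not use the pairing. If it means visits within a patient, the primary contrast has no power statement.

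**Working it through.** **1. The plan's own figure.** Inputs from SAP 5.1: difference 7 pg/ml, SD 15 pg/ml (given for basal IL-17 in patients), power 90%, alpha 0.05, taken as two-sided.

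Paired test, with 15 as the SD of the pair differences: n = (15 × (1.960 + 1.282) / 7)² = 48.3, so 49 pairs. The noncentral t gives 51 pairs, and 89.9% power at 50. The stated 50 is reproduced, but only on this reading. If each group has SD 15, a difference SD of 15 needs 2 × 15² × (1 − ρ) = 15², so a within-pair correlation of 0.5. The documents give no basis for one.

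**2. The test the SAP plans.** For independent groups, SE = 15 × √(1/n₁ + 1/n₂), assuming SD 15 in both. Power is from the noncentral t; the Mann-Whitney figures are simulated with normal data.

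| Patients / controls | SE (pg/ml) | 7 / SE | t test | Mann-Whitney |
|---|---|---|---|---|
| 50 / 50 | 3.00 | 2.33 | 64% | about 61% |
| 60 / 60 | 2.74 | 2.56 | 72% | about 69% |
| 80 / 60 | 2.56 | 2.73 | 77% | about 75% |

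Reaching 90% needs about 98 per group.

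**3. Possible confounding.** The documents give neither an expected age gap or sex imbalance nor any dependence of an analyte on age or sex. Everything in this step is assumed: no true group difference, age SD 11 years, within-group SD 1, linear age slope of 0.1, 0.2 or 0.3 SD per decade, 10,000 runs per cell.

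Bias = slope × (gap / 10) × 15 pg/ml. For example, 0.2 × 0.5 × 15 = 1.5 pg/ml.

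| Age gap | Bias (pg/ml) | False positives, 60 v 60 | False positives, 80 v 60 |
|---|---|---|---|
| 0 years | 0 | 5.1 / 4.7 / 5.1% | 5.0 / 4.7 / 5.5% |
| 3 years | 0.45 to 1.35 | 5.4 / 5.7 / 7.5% | 5.5 / 6.4 / 8.3% |
| 5 years | 0.75 to 2.25 | 5.4 / 8.0 / 12.3% | 5.5 / 9.4 / 13.8% |
| 10 years | 1.5 to 4.5 | 8.1 / 18.7 / 35.5% | 8.6 / 20.3 / 39.5% |

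The three rates are for the three slopes, unadjusted Mann-Whitney at 0.05. Sex alone (70% v 50% female, effect 0.2 to 0.5 SD) gives 5.5 to 8.2% at 60 v 60 and 5.6 to 8.3% at 80 v 60.

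A model with group, age and sex gives 4.6 to 5.4%. That is close to 5% by construction, because the assumed confounder is linear and is in the model.

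**4. A real difference can be hidden.** With a true 7 pg/ml, slope 0.2 and a 5-year gap acting against it, power at 60 v 60 is 49.5% for Mann-Whitney and 71.4% for the adjusted model (54.7% and 77.3% at 80 v 60).

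**5. Cost of adjusting when age does not matter.** With a true 7 pg/ml, adjusted power at 60 v 60 is 71%, 69% and 64% for gaps of 0, 5 and 10 years (77%, 75% and 69% at 80 v 60).

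**The case against.** The strongest reply is that the consequence is entirely assumed. At small gaps or weak slopes the rate stays near nominal, and the large figures need a 10-year gap with the steeper slopes. The simulation is normal and linear, while the SAP reports non-normal data. This stands: the documents establish exposure to confounding, not its size.

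A second reply is that the study is exploratory. No special hypothesis is planned, and 15 serum analytes at 0.05 each already give a 1 − 0.95¹⁵ = 54% chance of at least one false positive if they are independent. That multiplicity is a separate matter. Tests at 0.05 are still planned on the stated primary objective, and an exploratory label does not remove bias.

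Several stronger readings are tempting but not supported:
- **Controls will be older.** The missing upper age limit shows what is permitted, not who will be enrolled.
- **No matching was done.** The sample-size wording suggests that matching may have been intended. The documents show only that no factor, procedure or matched analysis is stated.
- **The whole set of control comparisons is primary.** The primary objective concerns serum levels, and Protocol 1.2 points to baseline. Flow cytometry lies outside it. Control vs Visit 3 also carries six months of fingolimod, which age and sex adjustment cannot remove.
- **Data had been seen.** The past tense in SAP 6.5 makes this possible but does not prove it.

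**Conclusion.** The point holds for serum Control vs Visit 1 and should be corrected. That the test is unadjusted and matching undefined is clear from the documents. The size of any bias is unknown and may be small, so a reader should not infer that the comparison is wrong or that a false-positive rate of 35% or more is to be expected.

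The power mismatch does not depend on any assumed age or sex effect. It rests on SD 15 in both groups, a 7 pg/ml difference and a two-sided 0.05 test. On those terms the stated 90% does not apply to the planned test at either size the documents name.

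Protocol 4.1 bars only MS in controls, while the synopsis, Protocol 4 and SAP 5 bar autoimmune disease. That is a separate editorial point and adds nothing to the weight of this one.

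**What to change.** 1. **SAP 6.5.1, serum Control vs Visit 1.** Add a model with group, age and sex on log concentration, with one rule for undetectable values fixed in advance. Report the adjusted ratio with its 95% CI. Keep Mann-Whitney and report both. Make the adjusted model the main analysis only if the control and patient data have not been seen; otherwise label it a post hoc sensitivity analysis. If a rank-based model is used, report its p-value only, since it gives no ratio in concentration units.
2. **Flow cytometry and Control vs Visit 3.** Apply the same model as secondary analyses. Do not read Control vs Visit 3 as an effect of MS alone.
3. **If matching was done.** State the factors and use a matched analysis in place of this model.
4. **Control age and sex.** State in Protocol 6.2 and Table 6-2 that both are recorded. SAP 6.1 needs them, but Protocol 6.2 speaks only of patients and Table 6-2 lists no demographics.
5. **Protocol 9.8 and SAP 5.1.** Restate the power for independent groups at the size meant, 60 or 80 patients, unless matching is defined and analysed.

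Cost: items 1 and 2 are SAP text. Item 4 and the Protocol 9.8 edit need a written amendment under Protocol 11.1. No new visits or samples are needed, but the model is possible only if control age and sex were recorded. It uses two degrees of freedom and loses some power if age differs between groups but does not affect the analyte (working, step 5).

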6.5.2 Flow Cytometry

Subjects' **IL-4, IL-6, IL-9, IL-10, IL-13, IL-17, IFN- γ and TNF- α** values will be tabulated by calculating mean and standart error and compared as Control group vs. Visit 1 (MS patients), Visit 1 (MS patients) vs. Visit 2 (MS patients), Visit 1 (MS patients) vs. Visit 3 (MS patients) and Control group vs. Visit 3 (MS patients) by using appropriate statistical test. Mann Whitney U test with significance level of 0.05 was used for the independent variables since non-normal distributions had been observed. Wilcoxon test was used for the dependent variables with non-normal distributions. For the independent variables with normal distributions Independent Sample t test was used whereas Paired sample t test was used for the dependent variables with normal distributions.

6.6 SAFETY ASSESSMENT

Incidence of AEs, incidence of SAEs and number of patients who died or experienced other serious or clinically significant events will be tabulated.
